Squamous cell cancer of the anus (SCCA) is one of the most common cancers among aging HIVinfected individuals in the United States. HIV-infected persons are at 40-80-times higher risk for SCCA than the general population, and recent cohort studies report that the incidence of SCCA among HIV-infected men is between 49-144/100,000 person-years, which is substantially higher than the incidence of cervical cancer prior to widespread screening with cervical cytology. The alarming increase in anal precancer and cancer in HIV- infected individuals has led to an increased emphasis on prevention. Current HIV primary care Guidelines (NY state HIV primary care guidelines, HIV Medical Association, and Infectious Diseases Society of America) both recommend annual anal cytology screening, with triage to high resolution anoscopy (HRA)-guided biopsy for histologic confirmation of anal high grade intraepithelial lesions (HSIL) among HIVinfected men who have sex with men (MSM), and certain HIV-infected women. However, HRAguided histologic diagnosis of HSIL is resource intensive, and has several drawbacks, including: extensive clinician expertise/training; pathology cost, availability, interpretation expertise; separate patient visits for diagnosis and treatment; and patient discomfort associated with unnecessary, non-neoplastic biopsies, given the low specificity of HRA-based visual HSIL identification. Our group has developed a portable, battery-operated, high-resolution microendoscope (mHRME) that provides subcellular images of the anal epithelium, delineating the cellular and morphologic changes associated with neoplasia. Our central hypothesis is that this 'optical' approach will increase the efficiency, clinical impact, and cost-effectiveness of the current standard of HRA-guided biopsy. In a recent pilot trial, the mHRME demonstrated a high sensitivity and specificity of anal HSIL diagnosis (94% and 92% respectively) compared to anal biopsy. Based on our significant preliminary data, we now propose to optimize and validate 3D imaging and HRME with a software interface that provides real- time image interpretation assistance, thus facilitating usage by less-experienced clinicians in community-based or low-resource settings. To validate this, we will conduct a study to determine the efficiency and diagnostic characteristics of an mHRME 'optical biopsy' approach versus the current standard of HRA-based tissue biopsy. In addition, we will construct, refine and analyze a disease model of HRA-based screening with mHRME to determine the cost- effectiveness of incorporating HRME into HRA-based HSIL diagnosis. Successful results will allow for improved efficacy and resource utilization for cancer screening in HIV-infected individuals for anal cancer and other epithelial cancers including the cervix, oral cavity, bladder, and GI tract.

1. STUDY OBJECTIVES

1.1 **Primary Objective**

To compare the diagnostic performance and efficiency of the optimized mHRME during HRA to standard of care HRA-guided anal biopsies. Using the optimized mHRME during HRA, we will evaluate the diagnostic performance (sensitivity, specificity, positive predictive value, negative predictive value) of mHRME optical diagnosis compared to paired anal tissue histology.

1.2 Secondary Objectives

a) To compare the diagnostic performance and efficiency of the optimized mHRME during HRA to standard of care HRA-guided anal biopsies. Using the optimized

mHRME during HRA, we will evaluate the efficiency (number of potential biopsies averted, reduction in procedure time)

b) To develop and optimize i) a mobile high-resolution microendoscope (mHRME) and 3D image mapping for anal HSIL diagnosis and ii) image-analysis software during HRA. To facilitate rapid interpretation and biopsy correlation in community-based settings, we will develop and test two innovative features: mHRME enhanced 3D-mapping, as well as anal HSIL automated image-analysis software for correlation of anoscopic and mHRME images to allow clinicians to identify areas of HSIL in real time in feasibility study.

2. BACKGROUND AND RATIONALE

2.1 Background

The alarming increase in anal precancerous and cancerous lesions among HIV-infected individuals, has led to an increasing emphasis on anal cancer prevention.6 The 2015 New York State HIV Primary Care Guidelines recommend annual anal cytology screening, with triage to high resolution anoscopy (HRA)-guided biopsy for histologic confirmation of anal high-grade intraepithelial lesions (HSIL) among HIV-infected men who have sex with men (MSM), and certain HIV-infected women.7 However, HRA-guided histologic diagnosis of HSIL is resource intensive, and has several drawbacks, including: extensive clinician expertise/training; pathology cost; separate patient visits for diagnosis and treatment; and patient discomfort associated with biopsies which are often negative or low grade.8,9 These drawbacks, in part, have led to limited adoption of anal cancer screening as evidenced by the fact that only 11% of HIV-infected MSM reported receiving screening in the preceding 6-12 months.10 Identifying novel, low cost, biopsy-free approaches which offer an accurate, real-time "optical biopsy" diagnosis could transform the current standard of practice by decreasing the numbers of procedures, reducing loss to follow up, and facilitating a "see and treat" approach.

Mobile High-Resolution MicroEndoscopy (mHRME) provides subcellular resolution of epithelial images, (up to transverse resolution of 4 microns) which delineates cellular and morphologic features (nuclear size, and pleomorphism) of epithelial neoplasia. Using this technology assisted by visual 3D mapping of the anal canal during anoscopy, clinicians will be able to localize all potential HSIL lesions and obtain "optical biopsies" of each documented lesion. Thus, this novel technology will allow for comprehensive documentation and accurate diagnoses of anal HSIL, thereby decreasing patient discomfort and procedure cost. The mHRME has already been shown to have high sensitivity and specificity with histologic diagnoses in other pre-cancer screening studies, including cervical 11 and esophageal squamous neoplasia.12 Furthermore, in preliminary data, HRME was shown to have a sensitivity of 93% and a specificity of 87% for anal HSIL detection.13 We propose to: 1) optimize the diagnostic performance of mHRME with 3D image maps for anal HSIL detection, followed by determiningthe of anal mHRME compared to the gold standard of HRA-guided biopsy. Our hypothesis is that mHRME plus 3D mapping will improve the accuracy and efficiency of HSIL diagnoses.

2.2 Study Rationale

Squamous cell anal cancer (SCCA) rates in HIV-infected individuals have continued to increase over the past decade despite the widespread use of cART.¹⁴⁻¹⁶ The availability of combined antiretroviral therapy (cART) has dramatically prolonged survival among HIV-infected individuals with life expectancy now approaching that of uninfected individuals.¹⁷⁻¹⁹ Driven by the aging HIV-infected population, and the fact that the incidence of SCCA has continued to increase in the cART era, ²⁰ SCCA has become one of the most common HIV-associated cancers.²¹ The highest risks appear to be among HIV-infected men who have sex with men (MSM) who have an increased SCCA risk of approximately 40-80 times greater than the general population, and an incidence of approximately 89/100,000 HIV-infected men. Women are also at increased risk for anal cancer (8-14 times greater than the general population), with a current incidence rate of approximately 18-30 per 100,000 person-years.^{4,20,22} The incidence of SCCA among HIV-infected MSM over the age of 60 is approximately 131/100,000 person-years, and the 10-year cumulative incidence of SCCA among men who have sex with men (MSM) over age 30 is approximately 1%.^{1,4,23-25}

Furthermore, SCCA leads to significant morbid effects in HIV-infected persons, who develop the disease at much younger ages (approximately 10 years younger) than uninfected persons ²⁶ and have higher rates of colostomy placement (in eventually >30% of cases),²⁶ higher rates of treatment failure,²⁷⁻³⁰ increased disease recurrence,³¹ and thus lower progression-free survival.³² These poor outcomes highlight the need to implement screening strategies for earlier detection.

HIV-infected individuals have a high prevalence of anal high-risk (HR) HPV infection and anal HSIL, leading to recommendations for anal dysplasia screening. HPV has been detected in 99% of cervical cancers and 80 to 90% of anal cancers, with HPV types 16 or 18 detected in about 70% of cervical and 80% of anal cancers.³³ Persistent anal HPV infection, in conjunction with other factors (smoking, history of advanced AIDS, and longer time period of detectable HIV viremia)³⁴ leads to the development of anal intraepithelial neoplasia grade 2 and 3 (AIN 2 and 3) also called anal high-grade squamous intraepithelial lesions (HSIL), a likely precursor to anal cancer. ^{35,36} In meta-analyses and recent reviews, the prevalence of HR-HPV infection and HSIL in HIV-infected MSM been shown to be 73.5% (48.9%-94.4%) and 29.1% (20.8%- 42.9%), respectively.³⁷ Among HIV-infected women, the prevalence of HR-HPV infection are somewhat lower at 43% (16%-85%),³⁷ but anal HSIL rates have been reported as high as a26% in another recent study.^{38,39} The rate of progression from anal dysplasia to invasive SCCA is also high;^{40,41} with estimates of HSIL progression to anal cancer in HIV-infected individuals ranging from approximately 1 in 263 to 377 cases per year.^{37,42,43} In a recent study of HIV-infected MSMs, 7% of 156 individuals with HSIL developed invasive anal cancer over a median period of 8.6 months.⁴⁴ Screening for anal cancer precursors is feasible and has been shown to be cost-effective.^{45,46} Several research and practice groups have recommended anal cancer prevention strategies focusing on anal cytology followed by anal colposcopy for both HIV-infected men and women because of the high rates of progression from anal dysplasia to invasive SCCA, and because SCCA shares many biologic properties with cervical cancer.⁴⁷ Currently, consensus on specific screening and treatment strategies are lacking, thus the development of optimal screening strategies based are critical. This proposal will provide a novel alternative surveillance tool that would substantially improve HSIL screening and surveillance strategies.

Current Screening for HSIL and Its Limitations:

The New York State guidelines for primary care of HIV-infected individuals recommend screening HIV-infected MSM and women with a history of CIN and condyloma yearly with anal Pap tests.⁷ If the cytology is normal, then the patient returns for routine screening again in one year. Because the specificity of anal pap smears is relatively low (ranging from 32%-59%), experts recommend performing anal colposcopy or high resolution anoscopy (HRA), a procedure similar to cervical colposcopy with acetic acid and Lugol's Iodine augmentation to identify high grade squamous intraepithelial lesions (HSIL), as the gold standard diagnostic test for any cytologic abnormality which includes: squamous cells of uncertain significance (ASCUS), low grade squamous intraepithelial lesions (LSIL), or high grade squamous intraepithelial lesions (HSIL).⁴⁹ At this time, current expert-guided anal dysplasia guidelines suggest either surveillance, ablative therapy (electrocautery, etc.) or topical treatment of anal HSIL because of the high rates of progression to invasive anal cancer among HIV-infected individuals.⁵⁰ Thus, with the current screening algorithm, patients need to return to the clinic at least three times from initiation of screening to HSIL treatment. Novel optimal imaging techniques, such as mobile high resolution microendoscopy (mHRME) to identify histologic HSIL could substantially simplify screening and surveillance algorithms.

In addition to the multiple visits needed for current anal dysplasia screening algorithms, the HRA procedure requires substantial training and expertise among practitioners. Anecdotally, the original group of researchers who brought HRA to the United States note a high degree of dexterity and technical prowess required to effectively visualize the entire anal canal and obtain reliable biopsy specimens.⁵¹ One study demonstrated that new HRA practitioners needed approximately 200 cases before demonstrating no missed high grade lesions found on follow-up.⁵² This substantial learning curve and the lack of practitioners trained formally in residency or fellowship has led to a scarcity of providers able to provide HRA. Due to both the low numbers of trained HRA practitioners, and the amount of health care resources needed to initiate an anal dysplasia screening program, anal cancer screening rates in HIV-infected individuals remain extremely low. For example, the CDC reported that only 11% (95% CI 9%-13%) of a nationallyrepresentative cohort of HIV-positive MSM (highest risk individuals) had an anal cytology test in the preceding year.¹⁰ Furthermore, a recent study found that among those who are screened, 35% of patients are lost to follow-up between HRA and biopsy and treatment.⁵³ Currently, there are several ongoing studies evaluating biomarkers for screening, and a large clinical trial called the ANal Cancer Outcomes Research (ANCHOR) evaluating the effectiveness of HSIL treatment on the incidence of invasive anal cancer. However, research focused on improving the visualization and diagnosis of HSIL through novel imaging technology are lacking.

Need for Low-Cost, High-Resolution Imaging: As HSIL treatment recommendations evolve, simplifying HSIL and/or early anal cancer screening, detection and surveillance will radically improve the access, cost and efficiency of anal cancer prevention. A robust, low-cost method of identifying HSIL or minimally invasive SCCA without need for biopsy would markedly improve existing HRA and histology-based diagnostic strategies. By offering an *in vivo* diagnosis, *more selective biopsies* can be performed. Additionally, the ability to delineate normal from neoplastic mucosa in real-time may *reduce the number of patients lost to follow-up* and *facilitate "see and treat" approaches using minimally-invasive ablative therapies.*⁵⁴⁻⁵⁶ We anticipate that the mHRME may enhance the efficiency and cost-effectiveness of current practice by preventing

unnecessary biopsies, repeat procedures, and loss of patients to follow-up. Successful results can easily be translated to other epithelial cancers: colon, cervix, stomach, etc.

3. STUDY DESIGN

This is a Device, Phase II, Multicenter, Cross-sectional Research Study with the following objectives:

4. SELECTION AND ENROLLMENT OF PARTICIPANTS

4.1 Inclusion Criteria

For all objectives:

- Consentable patients with documented HIV disease, and either previously documented HSIL or abnormal anal cytology within the past 2 years
- Ages 18 years and older
- Seen at the Baylor-affiliated Thomas Street Clinic (TSC), Mount Sinai Hospital and affiliated clinics

4.2 Exclusion Criteria

For all objectives:

- Patients with a platelet count less than 75,000 cells/mm3 and an absolute neutrophil count less than 1000 cells/mm3
- A known permanent or irreversible bleeding disorder that, in the opinion of the principal investigator (PI), would contraindicate any biopsy of the anal canal; current or prior history of anal cancer
- Allergy or prior reaction to the fluorescent contrast agent Proflavine or Iodine
- Patients who are unable to give informed consent.
- Patients who are pregnant

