4.3 Study Enrollment Procedures

This study involves recruitment of 200 HIV infected men and women with evidence of anal dysplasia from the Anal Dysplasia Clinics. This study will be available for enrollment at Thomas Street Clinic (TSC), Baylor College of Medicine and at the Mount Sinai Anal Dysplasia Clinic. In order to recruit these subjects, we will distribute information to both clinics and also physicians and their clinical staff who are in charge of the care of the subjects. The subjects will talk with their own physician who will describe the study, and arrange for an appointment. After their questions have been addressed, women who remain interested will sign the informed consent form. Potential participants will be approached by a trained research assistant (RA) to determine eligibility. Patients who participate in the study and are identified with anal disease will have access to appropriate ongoing care after study completion and will be offered remuneration for travel and inconvenience.

Potential subjects will read the informed consent. The consenting clinician will answer all their questions. The subject will be given a copy of the signed consent. The signed consent will be kept in a locked cabinet at the clinical site. We will explain all the procedures that will be performed, possible risks, benefits and alternatives.

Once the patient is enrolled, their information will be entered in the OnCoreTM Database System, which is a collection of interrelated tables that contain information on various aspects of enrollment activities. Information about human subjects will only be available to the research clinicians of the originating site. There is a potential loss of confidentiality at these gatherings, so participants will be counseled regarding the loss of confidentiality and this risk will be documented in the informed consent form.

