5. STUDY INTERVENTIONS

5.1 Interventions, Administration, and Duration

Study Drug – Proflavine Hemisulfate

Proflavine was used under FDA IND #102217; the HRME itself is an IDE-exempt device by the FDA. The contrast agent, proflavine, used in this study is the principal component of acriflavine and has been used for fluorescent imaging in the European, Asian and Australian gastrointestinal literature without any adverse events.

Study Intervention - mobile High Resolution Microendoscope (mHRME)

Patients will have mHRME images taken of Lugol's negative (abnormal) areas and subsequent standard-of-care HRA biopsies at each image site. In addition, there will be at least one extra image and biopsy taken at a Lugol's positive (normal) site. Each patient will likely have ≥ 2 biopsies. We plan to enroll 200 patients, which will yield 225-300 images.

Our approach uses topical contrast (proflavine) that directly highlights cell nuclei change, the most important pathologic marker of squamous cell intraepithelial neoplasia. In addition, we will implement image-analysis software to highlight these changes in real time, enabling less experienced practitioners to accurately recognize the hallmarks of neoplasia. The high-resolution fiber-optic microendoscope (mHRME) proposed for use here delivers 0.5 mW of 455 nm light to the tissue through a 0.8 mm diameter fiber- optic bundle, corresponding to an irradiance level of 100mW/cm2.

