6.2.1 Screening Evaluation

All patients scheduled for HRA will be screened for eligibility for the study at each clinic date.

Consenting Procedure

The research population will be identified from patients at Thomas Street Clinic and the Anal Dysplasia clinic at the Mount Sinai Medical Center ([name]) in New York City. The patient will be given information regarding the study and will be given the appropriate amount of time to carefully weigh the risks and benefits of the study. If the patient agrees to consent to participating in the study, the patient/participant will be counseled regarding all alternatives to study enrollment and regarding the right to withdraw consent at any time. In addition, the participant will be reassured that participation in the clinical trial will not in any way affect the future medical care received. The only document linking the participant and the research will be the consent form which will be filed in the subject's medical record.

Screening

The screening will be performed through secure electronic medical record system. The study investigators and study staff will make sure that personal information is kept confidential. All participant information will be stored securely in locked file cabinets in areas with access limited to study staff. All reports, study data collection, and administrative forms will be identified only by a coded number to maintain participant confidentiality. All local databases will be secured with password-protected access systems. Forms, lists, logbooks, appointments books, and any other listings that link participant ID numbers to other identifying information will be stored in a separate, locked file in an area with limited access.

Since [name] is a medical provider at TSHC, this temporary access to patients' PHI to determine eligibility does not constitute more than minimal risk and will not adversely affect the privacy rights and welfare of the individuals who are covered by the waiver. Since [name] is a medical provider at MSSM, this temporary access to patients' PHI to determine eligibility does not constitute more than minimal risk and will not adversely affect the privacy rights and welfare of the individuals who are covered by the waiver.

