7.2 Methods and Timing for Assessing, Recording, and Analyzing Safety Parameters

Upon completion of the study imaging, subjects will be contacted to screen for adverse events after a period of 2 and 30 days from procedure. Patients with abnormal clinical findings will be followed until the condition resolves or stabilizes. Adverse events or serious adverse events that occur during the follow-up period will be recorded regardless of relatedness to the study procedure. The safety follow-up may be conducted by a phone visit or a clinic visit; if clinically indicated, a clinic visit should be performed along with relevant lab work.

Patients will be contacted by phone at 1 and 2 years for follow up evaluation. See MOP for details.

We anticipate most AE/SAEs will be related to anoscopy (pain, bleeding). Proflavine has been administered to >1000 patients for use with HRME imaging

under [name] studies and we have had 0 related adverse events or serious adverse events.

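### Section 4.2 joins the platelet and neutrophil thresholds with 'and', so read literally it does not exclude a patient with only one low count

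*Combined protocol and SAP*

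**What the plan says.** Section 4.2, first bullet, excludes "Patients with a platelet count less than 75,000 cells/mm3 and an absolute neutrophil count less than 1000 cells/mm3". One subject governs both thresholds, and the word between them is *and*.

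The second bullet of 4.2 is the only other criterion that touches on bleeding. It excludes "A known permanent or irreversible bleeding disorder" where the principal investigator considers that it rules out an anal biopsy. It gives no platelet or neutrophil limit.

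Eligibility is a working step at two sites. Section 4.3 says "Potential participants will be approached by a trained research assistant (RA) to determine eligibility", and section 6.2.1 says "All patients scheduled for HRA will be screened for eligibility for the study at each clinic date". Section 9.3 restates the study population in brief and refers back to 4.1 and 4.2 for the criteria.

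On exposure, section 5.1 provides for standard-of-care biopsies at the imaged Lugol's-negative areas. It then says that, in addition, "there will be at least one extra image and biopsy taken at" a Lugol's-positive (normal) site. Section 7.3 names pain, bleeding and infection as the biopsy risks. It describes the biopsies as standard of care that the patient would have had without joining the study.

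**The concern.** A platelet limit and a neutrophil limit in a biopsy study guard against different harms: the first against bleeding, the second against infection. One low count is enough to raise one of those risks. A rule that acts only when both are low gives little protection against either.

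The exclusion is an operative safety criterion, applied by research staff during screening. If they follow the sentence as it stands, a patient with a single low count can be enrolled. Under 5.1 that patient then has at least one biopsy beyond standard care. Section 7.2 expects most adverse events to come from anoscopy, with pain and bleeding as its examples, so bleeding is a complication the plan itself foresees.

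**Working it through.** No figure in the plan is involved, so the check is of the logic of the criterion and of whether any other text restates or overrides it.

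**1. The rule as written.** Let P be the platelet count and N the absolute neutrophil count, both per mm3. As written, exclude if P < 75,000 *and* N < 1000. The alternative is to exclude if P < 75,000 *or* N < 1000. The values below are illustrations.

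| Example | P < 75,000? | N < 1000? | Excluded with *and* | Excluded with *or* |
|---|---|---|---|---|
| P 30,000, N 500 | yes | yes | yes | yes |
| P 30,000, N 2,000 | yes | no | **no** | yes |
| P 150,000, N 500 | no | yes | **no** | yes |
| P 150,000, N 2,000 | no | no | no | no |

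The two wordings differ in the second and third rows, the patients with exactly one low count.

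**2. Does another criterion catch those two rows?**
- Second row (low platelets only): the second bullet of 4.2 applies only if a bleeding disorder is already known, is permanent or irreversible, and is judged by the investigator to rule out biopsy. A reversible or undiagnosed low platelet count does not meet it.
- Third row (low neutrophils only): nothing in 4.2 applies.

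**3. Is the rule restated elsewhere?** Section 9.3 only points back. The Manual of Operations (Appendix 1), in its steps for seven days before clinic, names a chart check for iodine and proflavine allergy and no blood-count check. Platelets and neutrophils appear nowhere else in the visible text.

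**4. Does the drafting settle what *and* means?** It does not. Two places use *or* for alternatives: "Allergy or prior reaction to the fluorescent contrast agent Proflavine or Iodine" in 4.2 and "either previously documented HSIL or abnormal anal cytology within the past 2 years" in 4.1. But the site criterion in 4.1 joins the Houston clinic, the New York hospital and its affiliated clinics with *and*, and it must mean any one of them. The usage is mixed, so the literal reading is available and the looser one is plausible.

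**5. Is the extra biopsy standard of care?** Section 5.1 sets the Lugol's-positive biopsy apart from the standard-of-care ones. Section 7.3 treats all biopsies as ones the patient would have had anyway. The two statements do not agree for this biopsy.

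**The case against.** The best answer is that this is loose drafting which nobody would apply literally. The site criterion in 4.1 shows that these authors do use *and* for alternatives, and a clinician would naturally read two excluded groups. Clinicians also stand between the wording and any harm: the physician discusses the procedure with the patient, participants come from those already scheduled for HRA, and a standard-of-care plan is recorded for each lesion before biopsy. A patient with very low platelets would reach the study biopsy only if a physician was already prepared to biopsy. The CRF pages are not shown and may state the rule correctly.

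Much of this stands. It makes *either* the probable intent and makes the added risk incremental. It does not correct the text: none of those clinical steps mentions a blood count, and a CRF that says *or* would simply disagree with the protocol.

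Some stronger readings are tempting but unsupported:
- A reader might infer that *and* cannot be taken as *or* here. The site criterion in 4.1 shows that it can.
- A reader might infer that the sites apply the rule differently, or that unsuitable patients are being enrolled. Nothing in the documents shows either.
- A reader might put a number on it. If each low count is assumed to occur in 3% of patients, independently, then 200 × 2 × 0.03 × 0.97 = 11.64 per 200 screened have exactly one; if the two always occur together, the answer is 0. Both the rate and the overlap are assumptions, and patients screened are not patients biopsied, so the figure carries no weight.
- A reader might infer that participants are not told about the extra biopsy. The consent pages are not part of the review text, so this cannot be judged.

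**Conclusion.** The point holds as a wording error in a safety criterion. On its literal reading the first bullet of 4.2 lets through patients with one low count, and no visible text closes that gap. This conclusion rests on the sentence itself and on the absence of any restatement; it does not depend on an assumed rate.

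Its size in patients cannot be estimated from the documents. The consequence is confined to participant safety and to eligibility being read the same way at both sites. The sample size, the endpoints and the sensitivity, specificity and predictive-value estimates are untouched. There is no sign that requiring both counts was a deliberate choice, so it should be treated as a correction and not as a dispute over design.

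**What to change.** In 4.2, change the first bullet so that either a platelet count below 75,000 cells/mm3 or an absolute neutrophil count below 1000 cells/mm3 excludes the patient, or make it two bullets. If the sponsor does intend both, say so expressly and give the reason. Confirm that the CRF page recording eligibility and the practice at both sites use the same rule.

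In 7.3, add a sentence saying that the Lugol's-positive biopsy required by 5.1 is done for the study and is not standard of care.

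The cost is one word and one sentence in an amendment to the single IRB. There is also a practical cost. Under *and*, one count at or above its limit is enough to clear a patient; under *or*, both counts must be on record, so some patients may need a further blood test. A few patients may be lost to recruitment, in a number that the documents do not allow to be estimated.
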